Research coordinators will approach all patients at day 0 of intravenous antibiotic treatment for a pulmonary exacerbation to obtain consent, determine eligibility and to complete a Data Collection Form. If the participant is female and post-menarchal, a pregnancy test will be done at day 7 before randomization to prednisone or placebo. If the test is positive, the participant is ineligible for randomization. If the test is positive, the participant and her primary care CF physician will be informed of the result in private. Every effort will be made to keep any pregnancy test results private.

All study sites will perform pulmonary function tests at day 7 of IV antibiotic therapy for a pulmonary exacerbation as part of clinical care. If based on day 7 pulmonary function testing (± 2 days), a patient has not recovered $>90\%$ of their baseline FEV_1 % predicted (Non-Responders), they will be randomized into the placebo or prednisone treatment arm (**Figure 2 Randomization Flow Chart**). Baseline lung function will be defined as the best FEV_1 in the 6 months prior to the PEx (or in the 12 months prior to PEx if there are no measurements in the 6 months prior) (3). Patients who achieve $>90\%$ of their baseline FEV_1 % predicted at day 7 (Responders) will not be randomized to prednisone or placebo but will continue in the study as outlined below.

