Patients will be randomized to receive either oral prednisone 2 mg/kg/day (max 60 mg; rounded to the nearest 10 mg) (Table 1) divided twice daily or oral placebo twice daily for 7 days in addition to the IV antibiotics prescribed by their physician (**Randomization**). On Day 7 only, it may be necessary on some occasions when the study drug (prednisone or placebo) is not available until the late afternoon, to give the study drug as one full dose (as opposed to twice daily). The choice and duration of antibiotic therapy will be left completely to the discretion of their treating physician. Study outcome measures will be obtained for all enrolled subjects at day 0 (± 2 days) and subsequently at day 7 (± 2 days), day 14 (± 2 days) of IV antibiotic treatment and at the 1 month follow up visit (approximately 1 month after day 14), as per usual standard of care (; **Table 2 Study Design Schedule**). However, day 0 may + 3 days when impacted by a Friday or long weekend admission/IV antibiotic start time. Patients who are receiving home IV antibiotic therapy for a PEx will also be eligible as they return to clinic weekly according to standard clinical care.

During the course of their admission, for patients willing to provide samples, the following specimens will be collected for the bio-repository for future analysis. All biological samples will be labeled using the patient's study number. The patient's study number will be linked to patient identifiers only by a master list that is managed by the PI and the Research Coordinator of this study:

- Sputum for inflammatory markers— For patients who can produce sputum, we will collect a research sputum sample which will be immediately sent on ice to collaborator [name] laboratory for processing for inflammatory markers and stored for future examination of biomarkers according to the standardized protocols developed by the Therapeutic Drug Network, US CF Foundation.

- Serum for biomarkers—Blood collection for future studies will occur at the time of clinical bloodwork or if a patient chooses to provide research blood separately. A total of 8 mls of blood will be drawn in two lavender top EDTA tubes in the phlebotomy clinic, stored on site and subsequently delivered to [name] laboratory at St. Paul's Hospital (a sub-site for the study) for final processing and storage.

Randomization and distribution of drug/placebo

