Randomization (1:1) will be done through central allocation of a block-randomization schedule prepared through a computer-generated random listing. Randomization will be done by the study data analyst at the Hospital for Sick Children. The analyst will be the only member of the investigative team aware of the randomization assignment and will not be directly doing the statistical analysis. He/she will not be involved in the care of the study patients or the measurement of outcomes in the study. No other research staff nor patients nor physicians will be aware of the randomization assignment. The pharmacist at each study site will call the analyst for randomization.

Once the patient is randomized, the analyst will inform the research pharmacy at each study site and they will distribute either prednisone or placebo (lactose, packaged in #0 capsules of identical appearance) to the hospital ward or the CF clinic according to dosing Table 1. Physicians and patients will be blinded to the treatment, and placebo will be produced to look identical to the treatment drug. The microbiology lab and pulmonary function lab will also be blinded to the treatment allocation. Compliance will be measured by nurses for hospitalized patients and by asking patients to return any unused medication for patients receiving homecare IV antibiotics.

Safety monitoring

Patients who are most at risk of developing side effects secondary to corticosteroid use will be excluded based on the above exclusion criteria. Subjects will be monitored with measurements of urine glucose on day 7, day 10 (\pm 2 days) and on day 14 of antibiotic treatment while on prednisone (or placebo). If the urine glucose is $> 2+$, a serum glucose measurement will be performed. All the information will be provided to the treating physicians; they can decide at any time to withdraw their patient and request unblinding of the treatment allocation. The study will be monitored by a Data Safety Monitoring Board (DSMB) (Appendix 1.2-Data Safety Monitoring Plan).

E. Study outcomes:

Primary outcome:

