The questionnaire that will be used is the Cystic Fibrosis Questionnaire-Revised (CFQ-R) Respiratory domain (44). The CFQ-R is a disease-specific instrument that measures health-related quality of life for adolescents and adults with CF with a developmentally appropriate version for children. The CFQ-R is a reliable and valid measure of quality of life for individuals with CF and is frequently used in clinical trials to assess the effects of new therapies (45). In addition, subjects will also be asked to complete the CF Respiratory Symptom Diary (CFRSD) on day 0, day 7, day 14 and at the 1 month follow up visit(46). The Chronic Respiratory Infection Symptom Score will be applied to the CFRSD to calculate a severity score from 0-100 (100 being most severe). The CRISS score has been previously shown to be a responsive measure of steroid treatment effect in CF pulmonary exacerbations(47).

iv)The length of hospitalization and duration of IV antibiotic treatment in each treatment arm.

Length of hospitalization (number of days in hospital) and duration of IV antibiotic treatment are clinically relevant and patient-meaningful outcomes that will be calculated for each patient and compared between treatment groups.

v) The time to subsequent PEx in each treatment arm.

Based on our previous study, we know that the time between exacerbations is one of the most important determinants of overall lung function decline in an individual with CF (6). Time to subsequent pulmonary exacerbation will be calculated from the last day of IV antibiotic therapy of the randomized exacerbation to the first day of re-starting IV antibiotic treatment for a new pulmonary exacerbation (minimum 21 days between events). We will compare the average (or median if data not normally distributed) duration between treatment groups. We will follow up patients for subsequent exacerbations for 1 year following their randomized exacerbation.

vi) The number of adverse events and withdrawals from study recorded in each treatment arm.

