When target sample size is reached, the study statistician (who will not be involved in the conduct of the study) will unblind the treatment allocation (identify who is in group A vs B but not identify the groups themselves as active drug or placebo) and estimate the treatment effect between the two groups based on the primary outcome (intention-to-treat). If there is a statistically significant treatment effect ($p<0.05$), the study statistician will do the following statistical analyses. For the primary outcome we will compare the proportion of randomized patients that responded at day 14 of therapy in the placebo arm compared with the treatment arm using a two sample test for proportions. We will perform intent-to-treat analysis according to the treatment arm subjects were randomized to. We will also perform a per-protocol analysis based on subjects who completed the 7 days of prednisone or placebo as per protocol. The same analysis will be performed for the proportion responding to therapy at 1 month. Logistic regression analysis will then be performed to adjust for potential confounders, such as age, gender, *Pseudomonas aeruginosa* or methicillin-resistant *Staphylococcus aureus* (MRSA) infection and lower FEV₁, as these factors have been associated with failure to recover lung function after an exacerbation (3, 25). For the additional secondary outcomes, absolute change in pulmonary function tests, length of hospitalizations and change in sputum measurements,

we will use parametric (t-test), or non-parametric (Mann-Whitney) two sample comparison test. Linear regression analysis will be then performed to adjust for potential confounders, as listed above. Time to subsequent exacerbation will be compared using a Cox proportional hazard model. Potential confounders will be adjusted for in the Cox-proportional hazard model. All secondary outcomes will be analyzed both as intention-to-treat and per-protocol. All outcomes will be obtained for all subjects irrespective of whether they completed the study per protocol. In the case of missing data, we will perform the analysis on complete (complete case analysis). To determine whether diabetic patients have a different response compared to non-diabetic patients, we will perform a sensitivity analysis comparing return to baseline lung function in diabetics vs non-diabetics according to treatment group.

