If when the statistician estimates the treatment effect between the two groups (above), there is NOT a statistically significant treatment effect ($p>0.05$), the statistician will re-calculate the sample size based on the observed data from 84 participants, in order to determine what sample size is required to observe a statistically significant effect. This data will be provided to the DSMB who will decide whether or not to continue the study, based on feasibility and the clinical relevance of the treatment effect size. Appendix 1.1 includes detailed plans for the analysis of the extension study, which will be designed as an adaptive trial (52).

H. Potential Challenges and Alternative Approaches

The main challenge of this study is the large estimated treatment effect size. The future adaptive trial design, however, allows us the flexibility to calculate the necessary sample size based on observed data if the difference between groups is clinically but not statistically significant. These data will inform the decision whether to continue the trial with the addition of other centers in either Canada or the United States (Deliverables and Future Directions). Another challenge is the number of potential confounders influencing lung function recovery. We have designed this trial to be pragmatic, that is, reflective of real life conditions, as it is not possible to stratify based on all the variables that could affect response such as concomitant medications, hospital vs home IV therapy, choice and duration of antibiotic therapy. Therefore, we will collect all this information and sensitivity analyses will be done to determine whether these variables affect the results.

I. Personnel Requirements and Study Timeline:

We will require a research coordinator at each site over the study period (see Budget).

J. Knowledge Translation (KT):

We have developed a KT plan with the assistance of [name], scientific director of KT at the Hospital for Sick Children (Appendix). Our target audiences for the results of this study are CF clinicians, patients and researchers. We will partner with CF Canada to implement the following KT strategies for disseminating our results: publishing in an open-access journal for all audiences, presenting at national (Canadian Clinics conference) and international CF

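### Length of stay is compared in all randomised patients with no stated time origin, so patients already on home IV at randomisation dilute the difference

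*Combined protocol and SAP*

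**What the plan says.** Section E, secondary outcome iv, states: "Length of hospitalization (number of days in hospital) and duration of IV antibiotic treatment are clinically relevant and patient-meaningful outcomes". Both are to be calculated for each patient and compared between treatment groups. The text gives no start for either count and no rule for patients who are not in hospital, or for later admissions.

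Section D ties randomisation to the day 7 result: "If based on day 7 pulmonary function testing (± 2 days), a patient has not recovered" more than 90% of baseline FEV₁, the patient is randomised. The same section says "Patients who are receiving home IV antibiotic therapy for a PEx will also be eligible", and on IV treatment: "The choice and duration of antibiotic therapy will be left completely to the discretion of their treating physician".

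Section G lists "length of hospitalizations and change in sputum measurements" among the outcomes for which "we will use parametric (t-test), or non-parametric (Mann-Whitney) two sample comparison test", followed by linear regression. The confounders it gives as examples are age, gender, two infections and lower FEV₁; hospital or home setting is not among them. IV duration is not named in the list of tests.

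Section H says it is not possible to stratify on every variable that could affect response, including "concomitant medications, hospital vs home IV therapy, choice and duration of antibiotic therapy". These will be recorded and examined in sensitivity analyses.

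**The concern.** Study drug starts about a week into the episode. A patient who is at home by then, whether never admitted or already discharged, has a number of hospital days that prednisone cannot alter unless the patient is admitted later. Putting such patients in the main comparison has two effects. It averages the inpatient effect with near-zero effects, which shrinks the difference in days. It also mixes short and long stays within each arm, which adds variance.

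At stake is the reading of an outcome that the plan itself regards as meaningful to patients, and for which Section B cites shorter stays with steroids in a COPD exacerbation trial. A real shortening among inpatients could be understated in size and harder to detect.

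**Working it through.** **The plan's own figure.** The documents give no sample size, SD or effect for outcome iv. The only planned size is 84 (42 per arm) for the primary outcome, with 30% v 60% response, 5% two-sided and 80% power (two-sided is assumed; it reproduces the figure):

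n = [1.960·√(2·0.45·0.55) + 0.842·√(0.30·0.70 + 0.60·0.40)]² / 0.30² = (1.379 + 0.565)² / 0.09 ≈ 42.

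So 42 per arm is used below, with 1:1 allocation as in the plan ("Randomization (1:1) will be done through central allocation").

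**Assumptions, none from the documents.** Home-IV share at randomisation h: 0 to 30%. Post-randomisation inpatient days: gamma, mean 8 on placebo and 5.5 on prednisone (effect 2.5 days), SD 4. Hospital days before randomisation: uniform 5 to 9 for inpatients, uniform 0 to 7 for home patients. No later admissions.

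**Step 1: difference in days.** Home patients contribute zero effect, so the expected difference is (1 − h) × 2.5:
- h = 10%: 0.9 × 2.5 = 2.25 days
- h = 20%: 2.0 days
- h = 30%: 0.7 × 2.5 = 1.75 days

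This holds wherever the count starts, because a lead-in that is the same in both arms cancels.

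**Step 2: variance of total stay at h = 30%.** Inpatient variance is 16 + 4²/12 = 17.33; home variance is 7²/12 = 4.08. Mean total stay is 15 days (placebo inpatients), 12.5 (prednisone inpatients) and 3.5 (home).
- Placebo: 0.7·17.33 + 0.3·4.08 + 0.21·11.5² = 41.1
- Prednisone: 0.7·17.33 + 0.3·4.08 + 0.21·9² = 30.4
- SE = √((41.1 + 30.4)/42) = 1.305, and 1.75/1.305 = 1.34
- Power ≈ Φ(1.34 − 1.99) = 26%

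For post-randomisation days among inpatients, about 0.7 × 42 = 29.4 per arm remain. SE = 4·√(2/29.4) = 1.043, 2.5/1.043 = 2.40, and power ≈ Φ(2.40 − 2.00) = 65%.

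**Step 3: simulation** (6,000 trials per row; power in %, t-test/Mann-Whitney):

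| Home share | Difference, all patients (days) | Total stay, all | From randomisation, all | Total stay, inpatients | From randomisation, inpatients |
|---|---|---|---|---|---|
| 0% | 2.5 | 78/86 | 81/90 | 78/86 | 81/90 |
| 10% | 2.25 | 52/67 | 66/73 | 73/81 | 76/86 |
| 20% | 2.0 | 37/48 | 52/53 | 68/77 | 71/82 |
| 30% | 1.75 | 26/30 | 41/34 | 62/70 | 65/76 |

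**Step 4: separating the two causes.** The last two columns differ only in the start of the count: about 3 points on the t-test and 4 to 6 on Mann-Whitney. Most of the loss in the third column comes from including home patients. Restarting the count in everyone recovers part of the power but none of the lost days.

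**Step 5: IV duration.** Treatment length remains open after randomisation for home patients too. In the same simulation the difference in IV days stays at about 2.5 at every home share. Power (t-test) is about 77–78% from the start of IV treatment and 80–81% from randomisation.

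**Step 6: other inputs.** With an assumed 3-day effect and SD 5, the difference falls to 2.4 days at 20% home and 1.5 at 50%. With no home patients, power is 78.5% from randomisation v 75.4% from admission. Over effects of 2 to 4 days and SDs of 4 to 7, starting the count at admission costs about 0.5 to 5 points.

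**The case against.** The strongest reply is that total days per episode in all randomised patients is a legitimate intention-to-treat quantity, unbiased between arms and arguably what matters to patients and hospitals. Restricting to inpatients answers a different question in fewer people. That is fair, and it is why an all-patient figure should be kept. It does not supply the missing time origin or the rule for home patients.

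A second reply is that Section H already recognises hospital v home therapy and promises sensitivity analyses. This is partly an answer. Those analyses do not say where the count starts or who enters the main comparison, and settling that after unblinding would be data-driven.

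Third, the size depends on a home-IV share that the documents do not give. Appendix 1.2 speaks of randomisation at the time of hospitalisation, but also sets out monitoring for patients treated at home, so neither a low nor a high share can be read from it. This stands and limits confidence.

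A reader might also infer more than the documents support:
- That the plan counts from admission. Whole-episode counting is the plain reading, but no origin is stated.
- That the week before randomisation itself shrinks the effect. It cancels between arms, and only its spread adds a little variance.
- That IV duration is diluted in the same way. It is not.

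**Conclusion.** The point holds for length of stay, with moderate confidence. The time origin is undefined, and patients at home at randomisation enter a comparison that treatment can hardly influence. The difference shrinks by about the home-IV share, and under the assumed inputs power falls noticeably even at 10% home. If almost all patients are inpatients at randomisation, little is lost.

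It does not follow that a real shortening would probably be reported as no difference. At 10% home, Mann-Whitney power on total stay is still about 67%, and the share is unknown. There is no bias towards either arm and the primary analysis is untouched. This is a modest, worthwhile improvement to one secondary outcome. For IV duration, only the time origin and a named test are missing.

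**What to change.** In Section E (outcome iv) and Section G:
- Count hospital days and IV antibiotic days from randomisation.
- Make the main length-of-stay comparison among patients who are inpatients at randomisation. This status precedes treatment, so the comparison remains randomised. Alternatively, stratify or adjust the analysis for hospital v home status at randomisation. Stratum-specific estimates give the inpatient effect. A single adjusted coefficient removes the between-setting variance but still averages over home patients (about 1.75 days at 30% home in the example).
- Report post-randomisation hospital days in all randomised patients as well, with a stated rule for later admissions, so that admissions of home-IV patients are captured.
- Analyse IV days in all randomised patients, and name the test.
- Report total days descriptively.

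The cost is wording, plus the admission, discharge, IV and randomisation dates; no extra patients or visits. The downside is that the main length-of-stay result rests on fewer patients and applies to inpatients only.

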height using the NIH guidelines(56)) and will monitor for these adverse events (see below-Safety Monitoring Plan). In addition, all untoward medical occurrences, whether or not deemed causally related to study participation, will be recorded and site investigators will be asked to assess both severity and whether or not the adverse event was related to study participation. We will use the following grading scale to assess adverse events:

Adverse Event Category	Description
Mild	transient event, no treatment change, e.g. glucosuria
Moderate	treatment discontinued e.g. severe/sustained hypertension or hyperglycemia
Severe	severe: death, unexpected hospitalization

Given that subjects will be randomized at the time of hospitalization for a pulmonary exacerbation, we will monitor the time to subsequent exacerbation. If we observe a shorter time to subsequent exacerbation in one of the treatment arms, this will be reported to the DSMB.

Reporting of AEs

All adverse events will be recorded by the research coordinator and reported to the study site investigator as well as the PI ([name]), who will oversee close and continuous monitoring for safety concerns throughout the trial. All serious adverse events will be reported to Health Canada, based on the Health Canada Guidance: Adverse Drug Reactions (ADRs) Reporting Criteria. All serious and unexpected adverse events will also be reported to the REB at each study site as well the REB at the Hospital for Sick Children (as study sponsor) within 48 hours of their occurrence. Adverse events will also be reported to the Data Safety Monitoring Board (DSMB) (see below) in the form of regular reports submitted every 6 months. Serious adverse events will be reported to the DSMB within 48 hours.

Safety Monitoring Plan

Hospitalized subjects will be monitored on day 7, day 10 (+/- 2 days) and on day 14 with urine dip glucose measurements while on prednisone (or placebo). If the urine glucose is > 2+, a serum glucose measurement will be performed. All the information will be provided to the treating physicians; they can decide at any time to withdraw their patient and request unblinding of the treatment allocation. To unblind a subject, the research coordinator or physician will call the PI ([name]) at [contact] [name] or page [contact]

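### Time to next exacerbation is measured from the end of IV antibiotics, a date treatment can move, and its 21-day rule is too loosely worded to show which early restarts count

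*Combined protocol and SAP*

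**What the plan says.** Section E, secondary outcome v, runs the clock "from the last day of IV antibiotic therapy of the randomized exacerbation to the first day of re-starting IV antibiotic treatment for a new pulmonary" episode, with the qualifier "minimum 21 days between events". Follow-up is described as: "We will follow up patients for subsequent exacerbations for 1 year following their randomized exacerbation." No analysis from randomisation is planned. Nothing says which two dates the 21 days separate, or whether a restart at a shorter gap is merged with the first course, ignored or censored.

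Three other places bear on this:

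- **Section D (Study protocol)** randomises at about day 7 of IV therapy and leaves the end of that therapy open: "The choice and duration of antibiotic therapy will be left completely to the discretion of their treating physician."
- **Section E, secondary outcome iv**, compares that same duration between arms: "The length of hospitalization and duration of IV antibiotic treatment in each treatment arm."
- **Appendix 1.2** adds a safety use of the endpoint: "If we observe a shorter time to subsequent exacerbation in one of the treatment arms, this will be reported to the DSMB." It gives no definition of its own.

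Section G promises both intention-to-treat and per-protocol analysis of every secondary outcome and names a Cox model for this one. Section E speaks instead of comparing averages or medians. The time-zero problem arises under either method.

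**The concern.** A randomised comparison of time to event is protected when both arms are counted from the same point, normally randomisation. Here time zero comes later and depends on how the patient did in between. By listing IV duration as an outcome, the plan itself allows that prednisone may change it. A shorter IV course would then lengthen the measured interval even if the next exacerbation fell on the same calendar date.

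The 21-day rule raises a second question about the same endpoint. The weeks just after a 7-day steroid course are where a short-lived benefit would show. Some IV restarts in that period are not events under the rule, and its wording does not settle which.

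At stake are the reading of one secondary outcome and of any check under Appendix 1.2 that borrows its definition. Section E calls the time between exacerbations one of the most important determinants of lung function decline, so the result will be read closely.

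**Working it through.** **The plan's own figure.** The documents give no event rate, median, hazard ratio or power for this outcome. The only sample size is for the primary outcome: 30% vs 60%, 80% power, 5% significance (taken as two-sided).

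n per arm = [1.96·√(2·0.45·0.55) + 0.8416·√(0.30·0.70 + 0.60·0.40)]² / 0.30² = (1.379 + 0.565)² / 0.09 = 41.97, so 42 per arm and 84 in all, as stated. It serves below only as the arm size.

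**Step 1: the clock.** Let R be the calendar date of the next IV restart and E the last day of IV therapy. The plan records R − E. If prednisone moves E earlier by s days and leaves R alone, the record becomes R − (E − s) = (R − E) + s. The spurious gain is exactly s days.

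To turn this into a hazard ratio, assume:

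- placebo IV therapy ends on day 21, which is 14 days after randomisation on day 7;
- restart dates are identical in the two arms, with a constant hazard after day 21;
- follow-up ends 365 days after randomisation.

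Cox hazard ratios, prednisone vs placebo:

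| Assumed median | s = 2 days | s = 4 days | s = 7 days | Counted from randomisation |
|---|---|---|---|---|
| 120 days | 0.987 | 0.974 | 0.955 | 1.00 |
| 180 days | 0.990 | 0.979 | 0.964 | 1.00 |
| 270 days | 0.992 | 0.983 | 0.970 | 1.00 |

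**Step 2: the 21-day rule under two readings.** Take IV therapy from day 0 to day 14 and a restart on day 24. From end of IV to restart is 24 − 14 = 10 days, so it is not an event. From start to start is 24 days, so it is an event. The wording allows both.

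With a constant hazard, the share restarting within w days of stopping IV is 1 − 2^(−w/median). For the first reading w = 21. For the second, after a 14-day course, w = 21 − 14 = 7, and w falls to zero once the course lasts 21 days.

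| Assumed median | w = 21 | per 42 | w = 7 | per 42 |
|---|---|---|---|---|
| 120 days | 11.4% | 4.8 | 4.0% | 1.7 |
| 200 days | 7.0% | 2.9 | 2.4% | 1.0 |
| 300 days | 4.7% | 2.0 | 1.6% | 0.7 |

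These shares are the same in both arms, so by themselves they show lost events, not bias.

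**Step 3: what the rule could hide, as a hypothesis only.** Suppose the hazard in the first 21 days after IV therapy were doubled on prednisone and equal afterwards. With every restart counted, the hazard ratio would be 1.13, 1.10 and 1.09 at medians of 120, 180 and 270 days; if tripled, 1.27, 1.21 and 1.18. Under the end-of-IV reading it becomes 1.00 if early restarters are excluded, and 0.99 to 1.02 if their two courses are merged. No figure in the documents supports such an excess. The calculation shows only that the endpoint could not detect one.

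**The case against.** **Safety capture.** A reader might infer that early relapses disappear from the safety data. The documents do not support that. Section E and Appendix 1.2 grade hospitalisation as a severe event. Appendix 1.2 asks subjects to report a re-hospitalisation for an exacerbation as a serious adverse event, and serious events go to the DSMB within 48 hours. None of these routes has a 21-day gap. What remains is narrow: a restart given as home IV therapy has only general adverse event reporting. Nor does Appendix 1.2 say that its time-to-exacerbation check uses the Section E definition. That definition is merely the only one on offer.

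**Evidence for rebound.** Section B reports that the arms of the cited COPD trial no longer differed at 6 weeks. That is loss of a difference, not an excess of relapses. The plan also tests durability through lung function and symptom scores at 1 month.

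**Size of the clock effect.** It is small, no IV difference is predicted, and the physicians who stop IV therapy are blinded. All of this stands. Blinding, however, does not stop a real drug effect from bringing the stop date forward.

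**Purpose of the definition.** The interval between treatment episodes matches the plan's stated interest in time between exacerbations, and a gap rule separates a new exacerbation from a continued one. Counting from randomisation has its own feature: a patient still on IV therapy cannot have an event, so an arm with longer courses gains event-free time. These are good reasons to keep the present interval as a supportive analysis and to keep a defined gap in the main definition. They do not justify having no analysis from randomisation.

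**Conclusion.** The point holds as a limited one. Time zero for outcome v is a post-randomisation date that treatment can move, so the comparison is not the intention-to-treat comparison Section G promises. The distortion is one day per IV day saved, or a hazard ratio of about 0.96 to 0.99 for 2 to 7 days at an assumed 180-day median.

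The 21-day rule is under-specified. Depending on its meaning it removes about 5-11% or about 2-4% of patients' first restarts from this endpoint, at assumed medians of 300 to 120 days and a constant hazard; the lower range also assumes a 14-day course. The documents supply none of these inputs, and neither the direction nor the size of any difference between arms can be derived from them.

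The gap concerns this endpoint and any Appendix 1.2 check that adopts it. It does not extend to safety reporting as a whole, to the primary outcome or to N=84.

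**What to change.** In Section E, define outcome v as time from randomisation to the first IV restart for a new exacerbation, followed to 1 year from randomisation. Keep the end-of-IV interval as a supportive analysis.

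State which dates the 21 days separate and how a shorter gap is handled. Add a sensitivity analysis that counts every IV restart with no minimum gap.

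In Section G, name these analyses and reconcile the Cox model with Section E's comparison of averages or medians. In Appendix 1.2, say that the DSMB receives the randomisation-based version including all restarts.

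The cost is wording in three places. Outcomes iv and v already require the IV start and stop dates, so no visit or measurement is added. The downside is small: in the all-restarts version some events will be continuations of the same exacerbation, and from randomisation a patient still on IV therapy cannot have an event. Reporting the versions together shows how much either matters.
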